9.3 SAFETY ANALYSIS

Early adverse events within 30 days of procedure will be reported as the number of events divided by the number of enrolled subjects. Linearized rates will be used to summarize adverse events for the late (>30 days) post-operative period. The linearized rates will be calculated as the number of late events divided by the total number of late-subject years.

Percentages for the early events and linearized rates for the late events also will be calculated for all other complications observed in the trial.

Actuarial rates based on the method of Kaplan-Meier will be calculated for each of the safety endpoints at each of the follow-up time points.

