11.4 CLINICAL EVENTS COMMITTEE

The Clinical Events Committee (CEC) evaluates adverse events that are endpoint related. The CEC adjudicates events for their relatedness to the investigational device and/or the surgical procedure. The CEC will be composed of physicians familiar with the treatment of valvular heart disease and cardiac surgery who are not participating in the investigational trial.

The trial Sponsor will provide the CEC completed case report forms and any relevant source documentation/subject information as provided by the clinical site investigators. Trial Sponsor will insure that all information is de-identified before presenting to the committee. The CEC documents its findings or rulings on each event. All meeting minutes and supporting documentation are maintained by the CEC administrator with a copy provided to the trial Sponsor.

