AE262	VALVE THROMBOSIS - AORTIC ANY THROMBUS NOT CAUSED BY INFECTION ATTACHED TO OR NEAR AN OPERATED VALVE THAT OCCLUDES PART OF THE BLOOD FLOW PATH, INTERFERES WITH VALVE FUNCTION, OR IS SUFFICIENTLY LARGE TO WARRANT TREATMENT. VALVE THROMBUS FOUND AT AUTOPSY IN A SUBJECT WHOSE CAUSE OF DEATH WAS NOT VALVE RELATED OR FOUND AT OPERATION FOR AN UNRELATED INDICATION SHOULD ALSO BE COUNTED.
AE263	VALVE THROMBOSIS - MITRAL "
AE264	VALVE THROMBOSIS - PULMONARY "
AE265	VALVE THROMBOSIS - TRICUSPID "
AE.7	CARDIOVASCULAR - MISC
AE270	ANGINA, STABLE CHEST PAIN, TIGHT OR HEAVY FEELING IN THE CHEST, OR DISCOMFORT WHICH SPREADS FROM THE CHEST TO THE ARM, BACK, NECK, JAW, OR STOMACH, NUMBNESS OR TINGLING IN THE SHOULDERS, ARMS OR WRISTS, SHORTNESS OF BREATH, AND NAUSEA RELIEVED BY REST OR NITROGLYCERINE AND/OR CONFIRMED BY ECG. STABLE ANGINA IS ANGINA THAT IS CONTROLLED BY ORAL AND/OR TRANSCUTANEOUS MEDICATION.
AE271	ANGINA, UNSTABLE UNSTABLE ANGINA IS ANGINA, WHICH NECESSITATES THE INITIATION, CONTINUATION OR INCREASE OF ANGINA CONTROL THERAPIES THAT MAY INCLUDE: NITROGLYCERIN DRIP, HEPARIN DRIP, OR IABP PLACEMENT. THE TYPE OF ANGINA MAY INCLUDE, BUT IS NOT LIMITED TO: REST ANGINA, NEW ONSET EXERTIONAL ANGINA OF AT LEAST NEW YORK HEART ASSOCIATION (NYHA) CLASS III IN SEVERITY, RECENT ACCELERATION IN PATTERN AND INCREASE OF ONE NYHA CLASS TO AT LEAST NYHA CLASS III, VARIANT ANGINA, NON-Q WAVE MYOCARDIAL INFARCTION, OR POST-INFARCTION ANGINA.
AE272	ANNULAR DISSECTION DISSECTION OF THE VALVULAR ANNULUS EXTENDING INTO THE AORTA. ANNULAR DISSECTION OCCURRING WITHIN 30 DAYS OF THE INDEX PROCEDURE WILL BE CONSIDERED VALVE RELATED. SHOULD BE CONFIRMED BY IMAGING, OR DIRECT VISUAL INSPECTION.
AE273	AORTIC DISSECTION DISRUPTION OF THE MEDIA LAYER OF THE AORTA WITH BLEEDING WITHIN AND ALONG THE WALL OF THE AORTA. AORTIC DISSECTION MAY OCCUR IN THE ASCENDING THORACIC AORTA (TYPE A DISSECTION) OR IN THE DESCENDING THORACIC AORTA (TYPE B DISSECTION). DISSECTION SHOULD BE CONFIRMED BY IMAGING OR DIRECT VISUAL INSPECTION.
AE274	ARTERIAL DISSECTION DISRUPTION OF THE MEDIA LAYER OF AN ARTERY OTHER THAN THE AORTA WITH BLEEDING WITHIN AND ALONG THE WALL OF THE VESSEL. SHOULD BE CONFIRMED BY IMAGING OR DIRECT VISUAL INSPECTION.
AE275	CARDIAC ARREST CARDIAC ARREST DOCUMENTED BY ONE OF THE FOLLOWING: VENTRICULAR FIBRILLATION, RAPID VENTRICULAR TACHYCARDIA WITH HEMODYNAMIC INSTABILITY, ASYSTOLE.

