AE276	CARDIAC DECOMPENSATION AN INABILITY OF THE HEART TO MAINTAIN ADEQUATE CIRCULATION; IT IS MARKED BY DYSPNEA, VENOUS ENGORGEMENT, CYANOSIS AND EDEMA.

Clinical Investigational Plan
Protocol Number: 2010-03

AE CODE LIST	
CODE	DEFINITION
AE277	CARDIOGENIC SHOCK A CLINICAL STATE OF HYPOPERFUSION SUSTAINED FOR GREATER THAN 30 MINUTES, WITH EITHER SYSTOLIC BLOOD PRESSURE < 80 MM HG, AND /OR CARDIAC INDEX < 1.8 DESPITE MAXIMAL TREATMENT (FLUIDS) OR REQUIRING INTRAVENOUS INOTROPES AND/OR PRESSOR AGENT OR AN INTRA-AORTIC BALLOON PUMP (IABP).
AE.7	CARDIOVASCULAR - MISC (CONTINUED)
AE278	CHORDAE TENDINEAE DAMAGE
AE279	CORONARY ARTERY OSTIAL OBSTRUCTION OBSTRUCTION OF THE CORONARY OSTIA. SHOULD BE CONFIRMED BY IMAGING AND THE SOURCE OF THE OBSTRUCTION (AORTIC VALVE, THROMBUS, ETC. SHOULD BE REPORTED.
AE280	ENDOCARDITIS ANY INFECTION INVOLVING THE STUDY VALVE. THE DIAGNOSIS OF OPERATED VALVULAR ENDOCARDITIS IS BASED ON ONE OF THE FOLLOWING CRITERIA: (1) REOPERATION WITH EVIDENCE OF ABSCESS, PARAVALVULAR LEAK, PUS, OR VEGETATION CONFIRMED AS SECONDARY TO INFECTION BY HISTOLOGIC OR MICROBIOLOGIC STUDIES; (2) AUTOPSY FINDINGS OF ABSCESS, PUS, OR VEGETATION INVOLVING A REPAIRED OR REPLACED VALVE; OR (3) IN THE ABSENCE OF REOPERATION OR AUTOPSY, MEETING OF THE DUKE CRITERIA FOR ENDOCARDITIS [4]. MORBIDITIES ASSOCIATED WITH ACTIVE INFECTION, SUCH AS VALVE THROMBOSIS, THROMBOTIC EMBOLUS, BLEEDING EVENT, OR PARAVALVULAR LEAK, ARE INCLUDED UNDER THIS CATEGORY, BUT NOT COUNTED IN OTHER CATEGORIES OF MORBIDITY.
AE281	HEART FAILURE – ACUTE ACUTE HEART FAILURE DESCRIBES EXACERBATED OR DECOMPENSATED HEART FAILURE, REFERRING TO EPISODES IN WHICH A SUBJECT IS CHARACTERIZED AS HAVING A CHANGE IN HEART FAILURE SIGNS AND SYMPTOMS RESULTING IN A NEED FOR URGENT THERAPY OR HOSPITALIZATION.
AE282	HEART FAILURE – CHRONIC (CHF) AN EVENT IN WHICH THE HEART FAILS TO MEET THE CIRCULATORY REQUIREMENTS OF THE BODY UNDER DIFFERING PHYSIOLOGICAL CIRCUMSTANCES, AND/OR A STATE IN WHICH CARDIAC OUTPUT IS REDUCED RELATIVE TO THE DEMANDS OF THE BODY, ASSUMING THE EVIDENCE OF ADEQUATE VENOUS RETURN. EVENT IS CONFIRMED CLINICALLY OR BY DIAGNOSTIC TESTING.
AE283	HYPERTENSION – SYSTEMIC DEFINED AS BLOOD PRESSURE > 140 /90 MM HG FOR SUBJECT WITHOUT DIABETES OR KIDNEY DISEASE; >130/80 MMHG FOR SUBJECTS ON 2 OCCASIONS WITH DIABETES OR RENAL DISEASE. UNLESS DUE TO PRESENCE OF MEDICATION, E.G. BETA BLOCKERS FOR 10 YEARS

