AE284	HYPERTENSION – PULMONARY MEAN PULMONARY ARTERY PRESSURE THAT IS GREATER THAN 25 MMHG AT REST AND/OR GREATER THAN 30 MMHG DURING EXERCISE CONFIRMED BY SWAN GANZ CATHETER OR DIAGNOSTIC PLACEMENT IN THE PULMONARY ARTERY BED AND CONDITION REQUIRES MEDICAL INTERVENTION TO RESOLVE OR TREAT THE CONDITION.
AE285	HYPOTENSION ABNORMALLY LOW BLOOD PRESSURE. FOR AN ADULT, HYPOTENSION IS DEFINED AS BLOOD PRESSURE LESS THAN 90/50 MMHG.

AE CODE LIST	
CODE	DEFINITION
AE.7	
CARDIOVASCULAR - MISC (CONTINUED)
 
AN ACUTE MYOCARDIAL INFARCTION IS EVIDENCED BY ANY OF THE FOLLOWING:
 
 1. A RISE AND FALL OF CARDIAC BIOMARKERS (PREFERABLY TROPONIN) WITH AT LEAST ONE OF THE VALUES IN THE ABNORMAL RANGE (CK \geq 5X ULN) TOGETHER WITH AT LEAST ONE OF THE FOLLOWING MANIFESTATIONS OF MYOCARDIAL ISCHEMIA: 
 A) ISCHEMIC SYMPTOMS; B) ECG CHANGES INDICATIVE OF NEW ISCHEMIA (NEW ST-T CHANGES, NEW LEFT BUNDLE BRANCH BLOCK, OR LOSS OF R WAVE VOLTAGE); C) DEVELOPMENT OF PATHOLOGICAL Q WAVES IN 2 OR MORE CONTIGUOUS LEADS IN THE ECG (OR EQUIVALENT FINDINGS FOR TRUE POSTERIOR MI); D. IMAGING EVIDENCE OF NEW LOSS OF VIABLE MYOCARDIUM OR NEW REGIONAL WALL MOTION ABNORMALITY. 2. DEVELOPMENT OF NEW PATHOLOGICAL Q WAVES IN 2 OR MORE CONTIGUOUS LEADS IN THE ECG, WITH OR WITHOUT SYMPTOMS. 3. IMAGING EVIDENCE OF A REGION WITH NEW LOSS OF VIABLE MYOCARDIUM AT REST IN THE ABSENCE OF A NON-ISCHEMIC CAUSE. THIS CAN BE MANIFEST AS: A. ECHOCARDIOGRAPHIC, CT, MR, VENTRICULOGRAPHIC OR NUCLEAR IMAGING EVIDENCE OF LEFT VENTRICULAR THINNING OR SCARRING AND FAILURE TO CONTRACT APPROPRIATELY (I.E., HYPOKINESIS, AKINESIS, OR DYSKINESIS); OR, B. FIXED (NON-REVERSIBLE) PERFUSION DEFECTS ON NUCLEAR RADIOISOTOPE IMAGING (E.G., MIBI, THALLIUM).
AE286	MYOCARDIAL INFARCTION
AE287	MYOCARDITIS
AE296	PERFORATION - ATRIAL
AE297	PERFORATION - VENTRICULAR
AE289	PERFORATION - OTHER
AE290	PERICARDIAL EFFUSION - MAJOR
AE291	PERICARDIAL EFFUSION - MINOR
AE292	PERICARDIAL TAMPONADE - MAJOR
AE294	PERICARDITIS
AE295	CARDIOVASCULAR - OTHER

Clinical Investigational Plan
Protocol Number: 2010-03

AE CODE LIST	
CODE	DEFINITION
AE.8	GASTROINTESTINAL/HEPATIC
AE350	GASTROINTESTINAL – ESOPHAGEAL RUPTURE/TEAR ANY EVIDENCE OF PUNCTURE/DISSECTION/PERFORATION, VARICES OR OTHER DAMAGE TO THE ESOPHAGUS REQUIRING INTERVENTION.

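### Unstable angina code AE271 names non-Q-wave myocardial infarction, which can also meet infarction code AE286, and no rule says which code prevails

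*Combined protocol and SAP*

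**What the plan says.** Appendix 15.1 defines AE271 (unstable angina) by the need for treatment: "UNSTABLE ANGINA IS ANGINA, WHICH NECESSITATES THE INITIATION, CONTINUATION OR INCREASE OF ANGINA CONTROL THERAPIES". It then lists types of angina that this may include, ending with "VARIANT ANGINA, NON-Q WAVE MYOCARDIAL INFARCTION, OR POST-INFARCTION ANGINA".

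The same appendix defines AE286 (myocardial infarction) as follows: "AN ACUTE MYOCARDIAL INFARCTION IS EVIDENCED BY ANY OF THE FOLLOWING". Three criteria follow:

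- Criterion 1 is "A RISE AND FALL OF CARDIAC BIOMARKERS (PREFERABLY TROPONIN) WITH AT LEAST ONE OF THE VALUES IN THE ABNORMAL RANGE", together with at least one sign of ischemia. Ischemic symptoms alone suffice as that sign, as do "ECG CHANGES INDICATIVE OF NEW ISCHEMIA (NEW ST-T CHANGES, NEW LEFT BUNDLE BRANCH BLOCK, OR LOSS OF R WAVE VOLTAGE"; new Q waves are only one of the options.
- Criterion 2 is new pathological Q waves.
- Criterion 3 is imaging evidence of new loss of viable myocardium.

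In criterion 1 a parenthesis after the abnormal range gives CK at least 5 times the upper limit of normal, although troponin has just been named as the preferred marker.

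On analysis, Section 9.3 states: "Percentages for the early events and linearized rates for the late events also will be calculated for all other complications observed in the trial". Infarction and angina are not among the 12 safety endpoints of Section 7.3.1, so both reach the report by this route. On adjudication, Section 11.4 states: "The Clinical Events Committee (CEC) evaluates adverse events that are endpoint related".

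**The concern.** An adverse event list should send one clinical event to one code. Here the milder code names a form of the more serious event, and the more serious code accepts that same form. A site that files a non-Q-wave infarction as unstable angina is following the list as written.

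Elsewhere the list does settle such overlaps:

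- A TIA with an acute lesion on imaging is moved to stroke (AE250 and AE255).
- Morbidities that accompany active infection of the study valve "ARE INCLUDED UNDER THIS CATEGORY, BUT NOT COUNTED IN OTHER CATEGORIES OF MORBIDITY" (AE280).
- Regurgitation or stenosis of the study valve is redirected to structural or non-structural dysfunction.

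Angina and infarction closely parallel TIA and stroke, yet this pair has no rule. The baseline medical history form also treats non-ST-elevation infarction as a type of infarction. That category is not identical to non-Q-wave infarction, but the form points the other way from AE271.

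At stake is the infarction rate in the descriptive safety tables. Section 6.2 names infarction as a risk of both the valve and the operation, and Section 8.2 allows concomitant bypass surgery. If infarctions are filed only under AE271, the error has one direction: fewer infarctions and more angina.

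**Working it through.** The documents state no infarction rate, so there is no figure of the plan's own to reproduce. The check compares the definitions and then illustrates the size under stated assumptions.

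**Step 1: which codes a non-Q-wave infarction meets.**

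| Event without new Q waves | AE286 | AE271 |
|---|---|---|
| Angina needing therapy, biomarkers clearly abnormal on any reading | Met (criterion 1) | Met, named in the list |
| Angina needing therapy, new loss of viable myocardium on imaging | Met (criterion 3) | Met, named in the list |
| Angina needing therapy, troponin abnormal, CK below 5 times the limit, no imaging loss | Depends on how the CK parenthesis is read | Met, named in the list |
| No angina (silent, or under anaesthesia) | Criterion 1 or 3 possible | Not clearly met |

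In the first two rows both codes apply. In the third, if the CK figure defines abnormality whatever the marker, AE286 fails and, of the two codes, only AE271 matches. If the CK figure applies only when CK is the marker used, AE286 is met and the event falls under both codes.

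**Step 2: effect on the late linearized rate.** Let *s* be the share of infarctions that are non-Q-wave and *m* the share of those filed only as AE271. Then

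reported rate = true rate × (1 − *s* × *m*).

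Assume a true rate of 1.0 per 100 late subject-years, *s* between 0.4 and 0.7, and *m* between 0 and 1. None of these comes from the documents.

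- *m* = 0: 1.0 × (1 − 0) = 1.0
- *s* = 0.4, *m* = 0.5: 1.0 × (1 − 0.20) = 0.8
- *s* = 0.7, *m* = 1: 1.0 × (1 − 0.70) = 0.3

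The reported infarction rate can thus be anywhere from 0.3 to 1.0, and the angina rate is raised by the same events, at most 1.0 − 0.3 = 0.7 per 100 subject-years.

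For scale, 200 subjects (Section 9.1) followed for 5 years less the first 30 days give 200 × (5 − 30/365) ≈ 984 late subject-years. If 80% of that is achieved (an assumption), the figure is about 787. At 1.0 per 100 this is about 8 to 10 late infarctions, of which at most 0.7 × 8 to 0.7 × 10, about 6 to 7, could move.

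**Step 3: effect on the early percentage.** Section 9.3 divides early events by enrolled subjects. With 200 enrolled and *f* the assumed share of early infarctions filed only as AE271, reported % = 100 × true count × (1 − *f*) / 200.

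| True early infarctions (assumed) | *f* = 0 | *f* = 0.25 | *f* = 0.5 | *f* = 0.75 |
|---|---|---|---|---|
| 2 | 1.00% | 0.75% | 0.50% | 0.25% |
| 4 | 2.00% | 1.50% | 1.00% | 0.50% |
| 8 | 4.00% | 3.00% | 2.00% | 1.00% |

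**Step 4: double entry.** If one event is entered under both codes, the infarction rate is correct and only the angina rate is inflated. The forms ask for an adverse event form for each event, so one form with one code is the more natural practice, but nothing in the list rules out two.

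**The case against.** A reader might infer that the infarction rate *is* understated. The documents do not support that. AE286 captures non-Q-wave infarctions, and if sites use it for all of them there is no bias. The defect is an unresolved overlap whose effect depends on coding.

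A reader might also infer that AE271 is the only code open to a troponin-positive infarction with a modest CK rise. That rests on the strict reading of the CK parenthesis; the other reading is equally available. AE271 also requires angina that calls for therapy, so an infarction without angina does not plainly enter it.

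Further points on the other side stand:

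- Neither event is a listed safety endpoint, and no sample size, test or performance criterion uses either rate, so no decision rule is biased.
- Events are not lost. Both codes sit in the same cardiovascular group (AE.7), so the group total is unchanged if each event is entered once. Seriousness, causality, intervention and a free-text summary are recorded whatever the code.
- The adverse event form shows only the classification, and the documents do not say who assigns the specific code. Section 12.9.2 promises form instructions that are not in the file, and these might contain a precedence rule. Its absence is established for the code list only.

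These points limit the consequence but leave the overlap in place. Correction by the Clinical Events Committee is not assured, because its stated remit is endpoint-related events.

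**Conclusion.** The code list is wrong as written on this point: AE271 names an event that can also meet AE286, with no precedence rule. The possible results are an understated infarction rate with an overstated angina rate, double coding, or no effect. For an assumed true rate of 1.0 per 100 late subject-years, the reported rate lies between 0.3 and 1.0, the upper end being no misfiling. The range rests wholly on assumed shares and shows what the wording permits; it is not an estimate of what has happened. The ambiguity over the abnormal biomarker range in AE286 is a second, related fault and could leave some infarctions with AE271 alone. Severity is minor, since only descriptive tables of other complications are affected.

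**What to change.** In Appendix 15.1:

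1. Remove non-Q-wave myocardial infarction from the types listed under AE271.
2. Add a line that an event meeting AE286 is coded AE286 only.
3. Within AE286, reconcile the stated preference for troponin with the CK parenthesis, so that it is clear which level counts as abnormal for which marker.
4. Check any AE271 events already filed against AE286 and recode those that meet it. Section 5.2.3 reports 20 subjects already implanted under Version A, but the documents give no event data, so there may be none to recode.

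The cost is a few lines of text and a short review; Section 15 allows the appendices to be updated separately from the plan. The downside is that the reported infarction rate may become slightly less favourable.

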7.3.3 OTHER DATA

The following blood data also will be collected at baseline, 3 months, and at each annual visit:

Complete blood count (CBC): including White Blood Cell Count (WBC), Red Blood Cell Count (RBC), Hemoglobin (Hgb), Hematocrit (HCT), and platelet count (PLT), and plasma free hemoglobin.

Serum creatinine will be collected at baseline only.

Coagulation profile will be collected at baseline, discharge, 3 months, and at the 1, 3, and 5 year follow-up visits.

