8.3 EXCLUSION CRITERIA

The principal investigator at the trial site must exclude subjects if any of the exclusion criteria are present. The following are the criteria for exclusion from participating in the clinical trial:

- Requires emergency surgery³
- Has prior mitral, tricuspid or pulmonic valve surgery, which included implant of a bioprosthetic valve, mechanical valve, or annuloplasty ring that will remain *in situ*
- Requires multiple valve replacement/repair
- Requires a surgical procedure outside of the cardiac area (e.g. vascular bypass)
- Has aneurysm of the aortic root and/or ascending aorta requiring surgical intervention
- Has active endocarditis/myocarditis or endocarditis/myocarditis within 3 months to the scheduled aortic valve replacement (AVR) surgery
- Has renal insufficiency as determined by creatinine (S-Cr) level ≥ 2.5 mg/dL or end-stage renal disease requiring chronic dialysis at screening visit
- Has MRI or CT scan confirmed stroke, cerebrovascular accident (CVA) or transient ischemic attack (TIA) within 6 months (180 days) prior to AVR surgery
- Has acute myocardial infarction (MI) within 30 days prior to AVR surgery
- Has presence of non-cardiac disease limiting life expectancy to less than 12 months
- Diagnosed with hypertrophic obstructive cardiomyopathy (HOCM)
- Diagnosed with hyperparathyroidism
- Exhibits left ventricular ejection fraction $\leq 30\%$ as validated by diagnostic procedure within 30 days prior to AVR surgery
- Echocardiographic evidence of an intra-cardiac mass, thrombus, or vegetation
- Hemodynamic or respiratory instability requiring inotropic support, mechanical circulatory support, or mechanical ventilation within 60 days prior to AVR surgery

³ Emergent surgery – surgery is carried out on the referral day before the beginning of the next working day.

- Documented leukopenia ($WBC < 3.5 \times 10^3/\mu L$), acute anemia ($Hgb < 10.0 \text{ gm/dL}$ or 6 mmol/L), thrombocytopenia (platelet count $< 50 \times 10^3/\mu L$) or history of bleeding diathesis or coagulopathy
- Diagnosed with myxomatous disease/connective tissue disorders (e.g. Marfan's Syndrome)
- Has prior organ transplant
- Current or recent participation (within 6 weeks prior to surgery) in an investigational drug or device trial
- Was previously implanted with trial device⁴
- Pregnant (female subject of childbearing potential only), lactating or planning to become pregnant during the duration of participation in trial

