AE351	GASTROINTESTINAL – INFECTION SEVERE INFLAMMATION OF THE GASTROINTESTINAL TRACT INVOLVING BOTH THE STOMACH AND SMALL INTESTINE RESULTING IN ACUTE DIARRHEA AND VOMITING. SHOULD BE CONFIRMED BY CULTURE
AE352	GASTROINTESTINAL – OTHER OTHER GASTROINTESTINAL EVENT THAT DOES NOT FIT IN ONE OF THE OTHER GI/HEPATIC CATEGORIES.
AE353	LIVER FAILURE - ACUTE A SYNDROME DEFINED BY THE OCCURRENCE OF ENCEPHALOPATHY, COAGULOPATHY AND JAUNDICE IN AN INDIVIDUAL WITH A PREVIOUSLY NORMAL LIVER.
AE354	LIVER FAILURE - CHRONIC CHRONIC LIVER DISEASE CAUSES CAN BE ANY CONDITION THAT RESULTS IN THE GRADUAL DEGRADATION AND RENEWAL OF THE TISSUE CELLS WITH A BODY'S LIVER. THIS PROCESS USUALLY RESULTS IN FIBROSIS OR CIRRHOSIS. DIAGNOSIS MAY BE CONFIRMED BY ABNORMAL BLOOD ENZYMES AND/OR BIOPSY
AE355	HEPATIC COMPLICATION - OTHER OTHER LIVER EVENTS THAT DO NOT MEET THE DEFINITION OF LIVER FAILURE (E.G. LIVER DYSFUNCTION) REQUIRING HOSPITALIZATION OR MEDICAL INTERVENTION.
AE356	PANCREATIC COMPLICATION (PANCREAS) AN EVENT PERTAINING TO, CONNECTED WITH, OR AFFECTING THE PANCREAS REQUIRING HOSPITALIZATION OR MEDICAL INTERVENTION.
AE357	SPLENIC COMPLICATION (SPLEEN) AN EVENT PERTAINING TO, CONNECTED WITH, OR AFFECTING THE SPLEEN REQUIRING HOSPITALIZATION OR MEDICAL INTERVENTION.
AE358	BILIARY (GALLBLADDER) AN EVENT PERTAINING TO BILE OR TO THE GALLBLADDER AND BILE DUCTS, WHICH TRANSPORT BILE REQUIRING HOSPITALIZATION OR MEDICAL INTERVENTION.
AE359	ENDOCRINE COMPLICATIONS AN EVENT PERTAINING TO, CONNECTED WITH, OR AFFECTING THE ENDOCRINE SYSTEM REQUIRING HOSPITALIZATION OR MEDICAL INTERVENTION.
AE360	METABOLIC COMPLICATIONS AN EVENT PERTAINING TO, CONNECTED WITH, OR AFFECTING THE METABOLIC SYSTEM REQUIRING HOSPITALIZATION OR MEDICAL INTERVENTION.
AE.9	GENITOURINARY/RENAL
AE370	URINARY TRACT INFECTION (UTI) INFECTION THAT AFFECTS ANY PART OF THE URINARY TRACT THAT REQUIRE HOSPITALIZATION OR MEDICAL INTERVENTION.
AE371	VAGINAL INFECTION INFECTIONS AFFECTING THE VAGINAL AREA THAT REQUIRE HOSPITALIZATION OR MEDICAL INTERVENTION.
AE372	GENITOURINARY – OTHER OTHER GENITOURINARY EVENT NOT PREVIOUSLY DESCRIBED REQUIRING HOSPITALIZATION OR MEDICAL INTERVENTION.
AE373	RENAL DYSFUNCTION AN ACUTE EVENT OR WORSENING OF RENAL FUNCTION POST-OPERATIVELY (INCREASE OF SERUM CREATININE TO < 2.0 , AND < 2X MOST RECENT PREOPERATIVE CREATININE LEVEL) AND DOES NOT REQUIRE DIALYSIS.

Clinical Investigational Plan
Protocol Number: 2010-03

AE CODE LIST	
CODE	DEFINITION

AE CODE LIST	
CODE	DEFINITION

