AE.9	GENITOURINARY/RENAL (CONTINUED)
AE374	RENAL FAILURE – ACUTE AN ACUTE EVENT OR WORSENING OF RENAL FUNCTION RESULTING IN ONE OR MORE OF THE FOLLOWING: 1) INCREASE OF SERUM CREATININE TO >2.0, AND 2X MOST RECENT PREOPERATIVE CREATININE LEVEL. 2) A NEW REQUIREMENT FOR DIALYSIS POSTOPERATIVELY.
AE375	RENAL FAILURE – CHRONIC A PROGRESSIVE LOSS IN RENAL FUNCTION OVER A PERIOD OF MONTHS OR YEARS RESULTING IN A DIAGNOSIS OF STAGE 5 - CHRONIC KIDNEY DISEASE.
AE376	RENAL – OTHER OTHER EVENT THAT IS NOT RENAL FAILURE OR RENAL DYSFUNCTION THAT REQUIRES HOSPITALIZATION OR MEDICAL INTERVENTION.
AE.10	PULMONARY/RESPIRATORY
AE380	ATELECTASIS COMPLETE OR PARTIAL COLLAPSE OF A PREVIOUSLY INFLATED LUNG; INABILITY OF LUNG TO FULLY EXPAND.
AE381	HYPOXEMIA DECREASED PARTIAL PRESSURE OF OXYGEN IN BLOOD SOMETIMES SPECIFICALLY AS LESS THAN 60 MMHG (8.0 KPA) OR CAUSING HEMOGLOBIN OXYGEN SATURATION OF LESS THAN 90%.
AE382	PLEURAL EFFUSION - RIGHT EXCESS ACCUMULATION OF FLUIDS, SOMETIMES BLOOD IN THE PLEURAL SPACE, WHICH IS COMMON AFTER CARDIAC SURGERY. REPORTABLE WHEN IT BECOMES SYMPTOMATIC AND REQUIRES FLUID TO BE INTERVENTIONALLY REMOVED.
AE383	PLEURAL EFFUSION - LEFT "
AE384	PLEURAL EFFUSION - BILATERAL "
AE385	PNEUMOTHORAX ACCUMULATION OF AIR OR GAS IN THE PLEURAL CAVITY, OCCURRING BECAUSE OF DISEASE OR INJURY AND REQUIRING SURGICAL INTERVENTION, HOSPITALIZATION OR MEDICAL INTERVENTION TO RESOLVE.
AE386	PULMONARY EDEMA AN ABNORMAL ACCUMULATION OF FLUID IN THE LUNGS REQUIRING HOSPITALIZATION OR MEDICAL INTERVENTION TO RESOLVE.
AE387	PULMONARY HYPERTENSION MEAN PULMONARY ARTERY PRESSURE THAT IS GREATER THAN 25 MMHG AT REST AND/OR GREATER THAN 30 MMHG DURING EXERCISE CONFIRMED BY SWAN GANZ CATHETER OR DIAGNOSTIC PLACEMENT IN THE PULMONARY ARTERY BED AND CONDITION REQUIRES HOSPITALIZATION OR MEDICAL INTERVENTION TO RESOLVE.
AE388	PULMONARY REGURGITATION THE BACKWARD FLOW OF BLOOD FROM THE PULMONARY ARTERY, THROUGH THE PULMONARY VALVE, AND INTO THE RIGHT VENTRICLE OF THE HEART DURING DIASTOLE.
AE389	PULMONARY EMBOLISM - RIGHT CLINICAL EVIDENCE OF NEW EMBOLISM WITH CONFIRMATION BY LUNG SCAN OR PULMONARY ANGIOGRAPHY.
AE390	PULMONARY EMBOLISM - LEFT "
AE391	PULMONARY EMBOLISM - BILATERAL "
AE392	PULMONARY/RESPIRATORY - OTHER OTHER RESPIRATORY EVENT THAT IS NOT RESPIRATORY FAILURE.
AE393	RESPIRATORY DYSFUNCTION/INSUFFICIENCY DETERIORATION OF SUBJECT'S RESPIRATORY EFFORTS LESS THAN 24 HRS AFTER COMPLETION OF THE INDEX PROCEDURE.

Clinical Investigational Plan
Protocol Number: 2010-03

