- Birth date (DD/MMM/YYYY)

Birth date:

- Year (YYYY) and age

Year:

Age:

Gender:

- Male

- Female

Was a pregnancy test performed?

- Yes

What was the result?

- No

Why was the pregnancy test not performed?

Please specify:

Is the subject willing to identify their race/ethnicity? No Yes

Please indicate the subject's race:

Please specify:

Please indicate the subject's ethnicity:

Please specify:

E Edwards Lifesciences

Study

Doc#

Subject ID

Site

Visit Date

Status

Visit Name

Subevent#

CRF Name

Blank CRF

Subject height:

cm in

What is the subject's Canadian Cardiovascular Society (CCS) Angina Class?

What is the subject's current Left Ventricular Ejection Fraction (LVEF)?

%

What is the subject's baseline serum creatinine value (mg/dL)?

Is this value within the normal range? No Yes

Was this result clinically significant? No Yes

MEDICAL HISTORY (Part 1)

Rev B

CARDIOVASCULAR MEDICAL HISTORY / RISK FACTORS

Does the subject currently have or has the subject ever had the following diseases / conditions?

- No Yes Coronary Artery Disease (CAD)

Please indicate which native coronary vessels have $\geq 50\%$ narrowing:

- No Yes Left anterior descending (LAD) coronary artery
 No Yes Circumflex coronary artery
 No Yes Right coronary artery
 No Yes Left main coronary artery

- No Yes Carotid Artery Disease

Please indicate the severity of the disease:

- No Yes Peripheral Artery/Vascular Disease

Please indicate which symptoms the subject has experienced:

- No Yes Claudication
 No Yes $>50\%$ stenosis of any peripheral artery
 No Yes Aortic aneurysm

- No Yes Pulmonary Hypertension

What is the severity of the condition?

- No Yes Systemic Hypertension

Please indicate if the subject:

- No Yes Has a documented history of hypertension diagnosed and treated with medication, diet and/or exercise
 No Yes Has prior documentation of blood pressure >140 mmHg systolic or 90 mmHg diastolic for patient without diabetes or chronic kidney disease; or prior documentation of blood pressure > 130 mmHg systolic or 80 mmHg diastolic on at least 2 occasions for patients with diabetes or chronic kidney disease
 No Yes Is currently on pharmacologic therapy to control hypertension

- No Yes Cardiomyopathy

Please indicate the type of cardiomyopathy

Study Doc#

Subject ID Site Visit Date Status

Visit Name Subevent# CRF Name Blank CRF

No Yes Congestive Heart Failure (CHF)

No Yes Aortic Stenosis

No Yes Aortic Insufficiency

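### The renal dysfunction and acute renal failure codes are not complementary and no postoperative creatinine is scheduled, so the reported renal rates may be misclassified and incompletely ascertained

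*Combined protocol and SAP*

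**What the plan says.** Section 15.1 of the combined protocol and SAP holds the adverse event codes. AE373, renal dysfunction, is an acute event or postoperative worsening that does not need dialysis, qualified by "INCREASE OF SERUM CREATININE TO < 2.0 , AND < 2X MOST RECENT PREOPERATIVE CREATININE LEVEL". AE374, acute renal failure, is met by either of two limbs: "INCREASE OF SERUM CREATININE TO >2.0, AND 2X MOST RECENT PREOPERATIVE CREATININE LEVEL", or "A NEW REQUIREMENT FOR DIALYSIS POSTOPERATIVELY". AE376, the residual renal code, covers "OTHER EVENT THAT IS NOT RENAL FAILURE OR RENAL DYSFUNCTION THAT REQUIRES HOSPITALIZATION OR MEDICAL INTERVENTION". Neither AE373 nor AE374 gives a unit, and AE374 gives no comparison operator before 2X.

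On eligibility, section 8.3 excludes a subject who "Has renal insufficiency as determined by creatinine (S-Cr) level ≥ 2.5 mg/dL" or is on chronic dialysis for end-stage disease, so baselines up to 2.49 mg/dL may enter.

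On data, section 7.3.3 states: "Serum creatinine will be collected at baseline only". Table 3 agrees. On the case report forms (section 15.3) the only creatinine value is on the Demographics form ("What is the subject's baseline serum creatinine value (mg/dL"). The Blood Data form has no creatinine field.

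On analysis, section 9.3 states: "Percentages for the early events and linearized rates for the late events also will be calculated for all other complications observed in the trial". Renal dysfunction is among the risks of the operation listed in section 6.2. It is not among the 12 safety endpoints in section 7.3.1.

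**The concern.** The two codes read as a milder and a more severe grade of the same event, so every non-dialysis worsening ought to fall in one of them. It does not. AE374 needs two conditions together, and its complement is therefore that at least one of them fails. AE373 instead requires both to fail. Rises that cross one threshold but not the other lie between the codes.

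The renal dysfunction and acute renal failure rates under section 9.3 are built on these codes. A near-doubling to a high level can be missing from both, while AE373 states no minimum rise. The gap is widest for subjects who enter with the highest creatinine. Because no postoperative value is scheduled, no structured field exists from which an event could be found systematically or reclassified later.

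**Working it through.** The plan gives no renal event rate, so there is no figure to reproduce. The check applies the two rules as written.

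**Notation and assumptions.** Let b be the preoperative and p the postoperative creatinine, with p > b and no dialysis. I take the unit as mg/dL, from section 8.3 and the Demographics form, and read 2X in AE374 as at least twice.

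- AE373: p < 2.0 and p < 2b.
- AE374, creatinine limb: p > 2.0 and p ≥ 2b.
- Complement of AE374: p ≤ 2.0 or p < 2b.

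**Values meeting neither code.**

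- Gap A: 2.0 ≤ p < 2b, which exists when b > 1.0. For b = 1.5 it runs from 2.0 up to 3.0; for b = 1.8, from 2.0 up to 3.6.
- Gap B: 2b ≤ p ≤ 2.0, which exists when b ≤ 1.0. For b = 0.7 it runs from 1.4 to 2.0. At b = 1.0 it shrinks to the single value 2.0.

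| b | p | p/b | 2b | AE373 | AE374 |
|---|---|---|---|---|---|
| 1.0 | 1.9 | 1.90 | 2.0 | yes | no |
| 1.0 | 2.1 | 2.10 | 2.0 | no | yes |
| 1.8 | 3.5 | 1.94 | 3.6 | no (3.5 ≥ 2.0) | no (3.5 < 3.6) |
| 0.7 | 1.6 | 2.29 | 1.4 | no (1.6 ≥ 1.4) | no (1.6 ≤ 2.0) |
| 2.2 | 2.3 | 1.05 | 4.4 | no (2.3 ≥ 2.0) | no (2.3 < 4.4) |
| 1.00 | 1.01 | 1.01 | 2.00 | yes | no |

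**Baselines of 2.0 to 2.49.** Here p > b ≥ 2.0, so p < 2.0 is impossible and AE373 is empty. Without dialysis, AE374 needs p of at least 2 × 2.0 = 4.0 to 2 × 2.49 = 4.98. Every non-dialysis rise short of doubling meets neither code.

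**Sensitivity to the missing operator.** If 2X means strictly more than twice, only p = 2b moves: for b > 1.0 that value then meets neither code as well. Both gaps remain.

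**Illustrative size; every input is an assumption.** I took a lognormal baseline with median 0.9, 1.0 or 1.2 and log-SD 0.25, truncated below 2.5, and p/b equal to 1 plus an exponential with mean 0.3, 0.5 or 1.0. The share of rises meeting neither code is then about 5% to 21% of all rises, and about 20% to 44% of rises of at least 1.5 times baseline. If 20 of 200 subjects worsened (10.0%) and 10% to 30% of them fell in the gaps, AE373 and AE374 together would show 20 × 0.9 = 18 (9.0%) down to 20 × 0.7 = 14 (7.0%). Some of the 2 to 6 remaining subjects would appear under AE376; how many cannot be said.

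**The case against.** A reader might infer that many worsening subjects are left out, that the renal rates will be wrong, and that the database cannot show these events at all. The documents do not support any of these.

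- **Many.** The documents give neither a renal event rate nor a baseline creatinine distribution, and the number of subjects with baseline 2.0 to 2.49 is unknown.
- **Left out.** AE376 takes a gap case that leads to admission or treatment, and section 9.3 reports that code too. Such a case is reported under another label, not lost. Only untreated gap cases have no renal code.
- **Will be wrong.** AE373 has no stated minimum rise, so it could admit trivial rises while larger ones go elsewhere. Its creatinine wording does, however, qualify an acute event or worsening of renal function, and section 11.2.1 requires an untoward occurrence. A rise from 0.8 to 0.9 need not be reported in practice. The net direction of error is not determined.
- **Cannot show.** The Adverse Event form has a genitourinary and renal class, a laboratory-finding tick box and a free-text summary. Section 12.9.1 requires source notes on abnormal results, and section 12.9.3 requires test results to be open to the monitor. Routine creatinine values can support an event.

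Little depends on these rates: the trial is single-arm and descriptive, with no hypothesis test.

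What stands is the logic. AE376 does not put a gap case back into the dysfunction or failure rate. Free text and source notes are no substitute for a recorded value. The clinical events committee evaluates endpoint-related events (section 11.4), so it is no backstop for renal coding.

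**Conclusion.** The point holds in a limited form. That AE373 and AE374 leave gaps, and that AE373 is unreachable for eligible baselines of 2.0 to 2.49 mg/dL, follows from the definitions themselves. It rests only on the unit being mg/dL; neither reading of the missing operator removes the gaps. The consequence is that the section 9.3 rates for renal dysfunction and acute renal failure may be misclassified. Ascertainment may also be incomplete and may differ across the up to 6 sites, because it depends on unscheduled local testing.

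The number of subjects affected cannot be derived from the plan; the shares shown above are illustrations under stated assumptions. No named endpoint is touched. It is worth correcting because the correction is cheap, not because it threatens the main results.

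**What to change.** 1. Reconcile the two definitions so that they are exhaustive and mutually exclusive for reporting: AE373 becomes postoperative worsening of renal function, without dialysis, that does not meet AE374. By construction no such worsening then lacks a code, including a value of exactly 2.0 and subjects with baseline 2.0 to 2.49.
2. State the comparison operator for 2X in AE374 and the unit in both codes (mg/dL, as in section 8.3). State whether AE373 carries a minimum rise; any value is for the sponsor to set.
3. Add a field to the Adverse Event form for the creatinine value supporting any renal event, taken from existing hospital records.
4. Optionally, add creatinine to the discharge blood draw already in Tables 3 and 6. That gives a common postoperative value across sites, but not the in-hospital peak, which needs serial results or chart abstraction, and nothing after discharge.

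**Cost.** Items 1 and 2 are a code-list revision, and section 15 lets appendices be updated independently of the plan. Item 3 is one form field and some abstraction per renal event. Item 4 is one extra laboratory value per subject. Renal events already reported, including any among the 20 subjects implanted under Version A, would need recoding for consistency, and the reported dysfunction rate may rise. These are reporting categories only; no treatment rule changes.
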